the web server safe from intrusion. Additionally, a Secure Socket Layer Encryption certificate will be issued to help prevent Internet fraud. The implementation of SSLs (i.e., cryptographic protocols) aims to enhance security over the Internet. IT will conduct stringent testing of web applications prior to the implementation of eHealth Familias Unidas Primary Care to prevent any exploits from occurring and to ensure the confidentiality of participants.

ii) Control Condition

Participants randomized to the control condition continue prevention as usual. These participants will not be receiving any services from our staff. These participants will only be asked to complete a survey at each of the 5 time points: when they first enroll, and at 6, 12, 24, and 36 months. The adolescent will also be asked to provide a sample for an STI test during each of these time points.

(b) Assessments

After the intervention is complete, assessors will call the families to return to complete follow up assessments. The follow up assessments will occur on the University of Miami Miller School of Medicine Campus, at the clinic sites or at the homes of the participants. The follow up assessments collect the same data as the baseline assessment. All measures will be self-report and completed using survey software provided by the study team

(c) Data Collection

Demographics. A demographics form developed by the creators of Familias Unidas will be administered to caregivers and youth in order to collect information on contact information, age, date/place of birth, number of years residing in the U.S., parents' marital status, and family income.

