#### **11) Data and Specimen Banking\***

For STI measurement, a urine sample will be collected from the adolescent at each time point. Both the adolescent and the research assessor shall be present (at the same time) during the procedures outlined in this section. The procedures for the data to be stored or associated with each specimen are described below:

- (a) Both the adolescent and the research assessor shall keep the adolescent's urine specimen in view at all times before the specimen is sealed and labeled. If any of the specimen is transferred to another container, the research assessor shall ask the adolescent to observe the transfer and sealing of the container with a tamper-evident seal.
- (b) The research assessor shall place an identification label securely on each container. The label must contain the date, the adolescent's specimen number, and the adolescent's code number as the identifying information. The research assessor shall apply a tamper-evident seal on each container if it is separate from the label. The specimen bottle must be securely sealed to prevent undetected tampering.
- (c) The adolescent shall initial the identification label(s) on the specimen bottle(s) with his or her case ID in order to certify that the specimen was collected from him or her.
- (d) The specimen and chain-of-custody forms must be packaged for transfer to Quest laboratories. If the specimens are not immediately prepared for transfer, they must be appropriately safeguarded during temporary storage. The collected urine will be picked up by Quest laboratories a minimum of once per week.
- (e) While any part of the chain-of-custody procedures is being performed, the specimens and custody documents must be under the control of the involved research assessor. The assessor may not leave the collection site during the interval between presentation of the specimen by the adolescent and securing of the specimens with identifying labels bearing

the adolescent's specimen identification numbers and Case ID. If the involved assessor momentarily leaves his or her workstation, the sealed specimens must be secured or taken with him or her. If the assessor is leaving for an extended period of time, the specimens must be packaged for transfer to Quest laboratories and secured before the assessor leaves the collection site.

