## 12) Data Management\*

### (a) Data Analysis Plan and Power Analysis

**H1a:** *eHealth Familias Unidas Primary Care will be effective, relative to Care as Usual, in reducing the frequency of (past 90-day) drug use in Hispanic adolescents over time.*

This hypothesis will be analyzed using Latent Growth Modeling (LGM). Growth models can be expressed in terms that are identical to models using random coefficients regression, mixed models or multi-level models, where the first level fits each response in time to an individual-level growth model. The second level represents the condition effect on the slope of drug use. LGM analyses will test for differences in trajectories of drug use over the 5 assessment time points among the 2 conditions. As recommended by Raudenbush and Bryk, we will use 2-level analysis to determine whether the mean trajectories of drug use for eHealth Familias Unidas Primary Care and prevention as usual differ significantly over time. Data analysis for this hypothesis and all others will be conducted using Mplus (v 7.2).

Power. Mplus Monte Carlo simulation with 10000 replications was used to calculate the power for this hypothesis using a latent growth curve model framework with one covariate (i.e., condition assignment) and missing data. With 5 time points (0, 6, 12, 24 and 36 months) and assuming a 5% attrition rate at each assessment (also assuming equal sample size across both conditions), with 228 cases in each condition at baseline (or 185 at the final assessment timepoint in each condition), we have 80% power to detect a regression coefficient equal to 0.09 (effect size = 0.3) in the regression of the slope growth factor on intervention condition. This is considered slightly over a small (0.2) effect size.

**H1b:** *eHealth Familias Unidas Primary Care will be effective, relative to prevention as usual, in reducing the frequency of (past 90-day) unprotected sex in Hispanic adolescents over time.*

The analytic plan and power analysis for this hypothesis are similar to that of H1a.

**H1c:** *eHealth Familias Unidas Primary Care will be effective, relative to prevention as usual, in reducing STI incidence (specifically, the incidence of gonorrhea and chlamydia).*

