This hypothesis will be analyzed using a univariate logistic regression for the binary outcome, new diagnoses of STIs (Yes/No). STI incidence will be defined as a positive laboratory test result for a new chlamydia or gonorrhea infection at any of the four follow up assessment timepoints. In the analysis for this hypothesis, condition will predict STI diagnosis. The test of the hypothesis will be based on a Wald test comparing the intervention regression coefficient to its standard error. Additionally, the time of STI diagnosis will be included as a covariate in the logistic regression to test the robustness of the intervention's effect.

**Power.** According to CDC national statistics, the annual STI incidence rate is 3.16% for Hispanic adolescents aged 15 to 19. Thus, we expect the 3-year STI incidence rate in the control group to be approximately 9.2%. Using a one-sided Z test with pooled variance to test the difference between two independent proportions (assuming the same 5% attrition rate at each assessment timepoint), the study has over 80% power to detect a difference of 6.1% in STI incidence between the two conditions. This difference in proportions translates to an effect size of Cohen's  $h = 0.26$ , considered a small ( $h = 0.2$ ) to medium ( $h = 0.5$ ) effect size, according to Cohen (1988).

**H2a:** *Intervention effects on frequency of drug use will be partially mediated by improvements in family functioning over time.*

To test for mediation, we will use the "product of coefficients" test described by MacKinnon and colleagues, which is based on the distribution of the indirect effect of the intervention through the mediator (Cohen, 1988). This procedure tests whether the product of the coefficients from the intervention to the mediator (a) and from the mediator to the outcome (b) is significantly different from zero. Specifically, we will estimate paths between intervention and family functioning (a), and between family functioning and drug use (b). Because we have five time points, our first mediation analyses will fit bivariate growth curves for both family functioning and drug use and examine the role of the (latent) slope of family functioning on the slope of

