**26) Provisions to Protect the Privacy Interests of Subjects**

During the recruitment and electronic consent/assent process, and prior to the assessments, the subjects are told that information is private, confidential and only accessed by specific study personnel. The subject is given a case ID to further protect their identity. The subject is free to ask any questions, and the consent form has the contact information of the Principal Investigator should they have further questions and the phone number to the University of Miami's Human Subjects office.

Please refer to Section 12(b) Secure Data and Quality Control.

As described before, each follow-up visit will include screening for Neisseria gonorrhoeae (GC) and Chlamydia trachomatis (CT) as indicated by reported sexual risk behaviors and per local site clinical and public health standards. Adolescents will be encouraged to refer sexual partners for treatment.

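### The H1c robustness check adjusts for time of STI diagnosis, which is undefined for adolescents without a diagnosis, and the plan does not say how they are coded

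*Combined protocol and SAP*

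**What the plan says.** Section 12(a), under H1c, plans a "univariate logistic regression for the binary outcome, new diagnoses of STIs (Yes/No"), with condition as the predictor and a Wald test of its coefficient. A case is an adolescent with a new chlamydia or gonorrhea "infection at any of the four follow up assessment timepoints", so each adolescent contributes one record. The section then adds that "the time of STI diagnosis will be included as a covariate in the logistic regression", to test whether the intervention effect is robust.

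The supplied text gives no value of that time for an adolescent who is never diagnosed. It describes no visit-level or survival model, and it states no other robustness check for H1c. STI incidence is one of the three primary endpoints in Section 9(a).

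Section 10(c), Data Collection, defines STI incidence over all five assessments, baseline included. Section 12(a) uses the four follow-ups only.

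**The concern.** A covariate in a per-adolescent regression needs a value for every adolescent. Time of diagnosis exists only when the outcome is Yes, so any value given to the others has to be invented, and the invented value largely determines the result. It also arises after randomisation and is partly a restatement of the outcome.

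What is at stake is the check rather than the main test. Its purpose is to show that the H1c result holds up. As written, it yields either no usable condition effect or one that depends on a coding chosen after the data are seen.

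**Working it through.** **Inputs from Section 12(a).** 228 per condition at baseline; loss described as "assuming a 5% attrition rate at each assessment (also assuming equal sample size across both conditions"); control incidence 9.2% over three years; detectable difference 6.1 points, hence 3.1% in the intervention arm; follow-up at 6, 12, 24 and 36 months; power from a "one-sided Z test with pooled variance".

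**Assumptions not in the plan.** One-sided alpha 0.05. Diagnoses spread in proportion to interval length (6, 6, 12 and 12 of 36 months), so one third fall at 36 months. Loss unrelated to infection. Simulated figures use 100,000 trials unless noted, and a fit with no finite estimate counts as non-significant.

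**1. The plan's own figures.**
- Three-year incidence: 1 − (1 − 0.0316)^3 = 9.2%.
- Final size: 228 × 0.95^4 = 185.7 per arm, 371.4 in all.
- Cohen's h: 2·asin(√0.092) − 2·asin(√0.031) = 0.26.
- Pooled Z power at 185 per arm: Φ[(0.061 − 1.645·√(2 × 0.0615 × 0.9385/185)) / √((0.092 × 0.908 + 0.031 × 0.969)/185)] = Φ(0.80) = 79%. At alpha 0.025 it is 69%, so 0.05 is the level close to the stated 80%.

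**2. Who has a time of diagnosis.** Control 185.7 × 0.092 = 17.1; intervention 185.7 × 0.031 = 5.8. That is about 23 of 371, leaving about 348 (94%) without one.

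**3. What each possible coding does.**
- *Non-cases missing.* Only the 23 or so cases remain, all Yes. The outcome is constant and nothing can be estimated.
- *Non-cases coded 0.* Time above 0 is the same thing as being a case. Separation is complete (500 of 500 simulated trials).
- *Non-cases coded 36 months.* Everyone with a time below 36 is a case, so separation is quasi-complete. As the time coefficient diverges, those records are fitted perfectly and stop informing the condition effect. What remains is positives at 36 months against non-cases: 17.1/3 = 5.7 and 5.8/3 = 1.9, or 7.6 of 22.8 events.

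For the 36-month coding, among adolescents attending all four follow-ups:
- Log odds ratio = ln[(0.031/0.969)/(0.092/0.908)] = −1.15 (odds ratio 0.32), with or without the covariate, because each arm keeps one third of its cases.
- Standard error unadjusted: √(1/17.1 + 1/168.6 + 1/5.8 + 1/180.0) = 0.49.
- Standard error with the covariate: √(1/5.7 + 1/168.6 + 1/1.9 + 1/180.0) = 0.84.
- Wald z at expected counts: about 2.3 unadjusted and 1.4 adjusted, against 1.645.
- Simulated power: 80% unadjusted, 24% adjusted, with no finite adjusted estimate in about 15% of trials. The adjusted power runs from 12% if diagnoses are equal per visit to 47% if half fall at 36 months.

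*Non-cases coded at their last attended visit.* Among adolescents with at least one follow-up test, scoring dropouts without a positive as No, the model fits. The odds ratio is 0.31, power 79% against 82% unadjusted, and type I error 5.2% against 4.8%. If only adolescents attending every visit are analysed, this is the same as 36-month coding.

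**4. Unequal loss, as an illustration only.** Take no true effect and loss of 5% per visit in control against 10% in intervention. Early times then mark both cases and dropouts. The extra intervention dropouts look, to the model, like adolescents who should have been cases, and this pushes the condition coefficient towards benefit. With dropouts scored No, the false-positive rate of last-visit coding depends on the common incidence:

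| Common incidence | False-positive rate |
|---|---|
| 3.1% | about 14% |
| 6.15% | about 20% |
| 9.2% | about 25% |

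At 9.2% the unadjusted model gives 8.3% on the same data. Among adolescents attending all four follow-ups, the rates are 2.8% for last-visit coding and 4.7% unadjusted.

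**5. A model that does use time.** A discrete-time logistic hazard model at the plan's rates and equal loss gives odds ratio 0.32, power 82% and type I error 4.8%. Some visit has no events in 2.7% of trials.

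**The case against.** This is a supplementary check, and the authors may simply have meant assessment wave in a visit-level model. An analyst would notice the failure under three of the four codings. The fourth fits and performs almost as well as the unadjusted model under the attrition that the plan assumes. Its failure needs unequal dropout, which Section 12(a) does not assume.

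Much of that stands, and it limits the point. A reader might infer that the check cannot be run at all. That goes too far, because last-visit coding runs and gives sensible answers under equal loss. A reader might also take 25% as the expected false-positive rate. It is not: it needs unequal loss, a 9.2% rate in both arms and dropouts scored No.

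What does not stand is the appeal to intent. The sentence describes a covariate in the one-record-per-adolescent regression. Assessment wave, last attended visit and time of diagnosis are different variables, and the text names only the last.

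**Conclusion.** The point holds as a specification defect in the one robustness check that the supplied text gives for a primary endpoint. The covariate is undefined for about 94% of adolescents, the simplest codings fail, and the one that works is not the one written down. That much follows from the definitions alone. The loss of power to about 24% rests on the assumed alpha and timing of diagnoses; the 14% to 25% false-positive range is conditional on unequal loss.

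A reader might infer that the H1c conclusion itself is at risk. The documents do not support that: the primary test is the Wald test from the model without this covariate, and neither the sample size nor the power statement uses it. The point is worth fixing because it is cheap, not because the trial's main answer depends on it.

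**What to change.** Keep the unadjusted logistic regression as the primary H1c test and delete the time-of-diagnosis covariate. Deletion alone cures the defect.

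If a check that accounts for time is wanted, suggested text is: *As a robustness check, condition will be tested in a discrete-time logistic hazard model with one record per follow-up STI test up to and including the first positive, and indicators for visit. Adjacent visits will be merged if a visit has no events. A missed test contributes no record.* A time-to-first-positive model would also serve. The good behaviour of the discrete-time model was checked here only for dropout unrelated to infection.

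Reconcile the outcome window in Section 10(c) (five assessments) with that in Section 12(a) (four follow-ups), and state how adolescents positive at baseline are treated, since this fixes both the outcome and the start of the risk period.

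The cost is a sentence or two of SAP text and, if the check is kept, one data restructure and one extra model. The primary test and sample size do not change.

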First Efficacy Study of Familias Unidas in a School Setting. [name] and colleagues evaluated the efficacy of Familias Unidas in preventing adolescent drug use, cigarette use, alcohol use, and unprotected sexual behavior, relative to (1) an HIV preventive intervention and (2) a cardiovascular preventive intervention. Participants ( $n = 266$ , mean age = 13.4,  $SD = .68$ ) were assessed at baseline, randomized, and reassessed at 6, 12, 24, and 36 months post baseline. Familias Unidas was efficacious, relative to the cardiovascular intervention in reducing past 90-day illicit drug use ( $z = 2.02$ ,  $p < .05$ ), efficacious relative to both the HIV intervention ( $z = 3.25$ ,  $p < .002$ ) and the cardiovascular intervention ( $z = 2.66$ ,  $p < .008$ ) in reducing past 90-day cigarette use, and in reducing unprotected sexual behavior at last sexual intercourse ( $X^2(1) = 3.87$ ,  $p < .05$ ). The effects of Familias Unidas were partially mediated by improvements in family functioning. Finally, post-hoc analyses also showed that the incidence of (self-reported) STIs in Familias Unidas was significantly lower than for adolescents in either of the two control conditions (Fisher's Exact  $p$ -value = .05).

Second efficacy study of Familias Unidas in a School Setting. [name] and colleagues evaluated the efficacy of Familias Unidas in preventing adolescent substance use as well as unprotected sexual behavior, relative to prevention as usual in a sample of behavior problem youth. 213 participants (mean age =14.3,  $SD =0.7$ ) and their primary caregivers were enrolled. Participants were assessed at baseline, randomized, and reassessed at 6, 18, and 30 months post baseline. Analyses showed a significant difference in past 30-day substance use ( $b=0.53$ ,  $z =2.42$ ,  $p < .02$ ;  $d =0.25$ ) and in the frequency of condom use ( $b= -0.306$ ,  $z = -2.214$ ,  $p<.03$ ;  $d =0.30$ ) between Familias Unidas and prevention as usual.

Third efficacy study of Face-to-Face Familias Unidas in a School Setting. [name] and colleagues evaluated the efficacy of Familias Unidas in reducing past-90 day illicit drug use and unprotected sexual behavior, relative to prevention as usual, among adjudicated Hispanic youth. 212 (mean age = 14.6,  $SD = 1.36$ ) juveniles and their primary caregivers were assessed at baseline and reassessed at 6 and 12 months post baseline. The results showed that Familias Unidas was efficacious, relative to

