- Frequency of (past 90-day) unprotected sex in Hispanic adolescents over time.
- STI incidence (specifically, the incidence of gonorrhea and chlamydia).

ii) Secondary:

- Improvements in family functioning over time (e.g. parent-adolescent communication, parental monitoring of peers).
- Frequency of unprotected sex will be partially mediated by improvements in family functioning over time.
- Reduction of STI incidence will be partially mediated by improvements in family functioning and decreases in unprotected sex over time.

(b) Safety endpoints

Not applicable.

10) **Procedures Involved**

(a) Study Design

This study tests the effectiveness of eHealth Familias Unidas Primary Care in preventing drug use, unprotected sexual behavior, and STIs in a universal sample of Hispanic youth, this study will use a randomized trial design with two levels of intervention (eHealth Familias Unidas Primary Care and prevention as usual) as the between subjects factor with five repeated measures assessments at baseline, 6, 12, 24, and 36 months post baseline as the within subject factor.

Once both primary care giver and adolescent have completed the consent/assent, they will complete the baseline assessment electronically. Once the baseline assessment is complete, they will be randomized to one of the two conditions: eHealth Familias Unidas Primary Care (experimental prevention as usual (control) Condition. Please see attached for consent/assent forms (in English and Spanish). All consent forms will be completed electronically. All confidential study participant information will be stored electronically in secure University of Miami systems.

i) eHealth Familias Unidas Primary Care

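### The H1c power calculation uses a compounded 3-year incidence of 9.2%, but the endpoint counts only infections still detectable at four scheduled urine tests

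*Combined protocol and SAP*

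**What the plan says.** The H1c paragraph of section 12(a) defines the outcome as a "positive laboratory test result for a new chlamydia or gonorrhea infection at any of the four follow up assessment timepoints". Section 10(a) places the assessments "at baseline, 6, 12, 24, and 36 months post baseline", so the gaps between tests are 6, 6, 12 and 12 months. Section 11 specifies one urine sample at each time point, and section 10(c) a PCR that detects the organisms' DNA.

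The power paragraph for H1c starts from outside statistics: "the annual STI incidence rate is 3.16% for Hispanic adolescents aged 15 to 19". It continues: "Thus, we expect the 3-year STI incidence rate in the control group to be approximately 9.2" per cent. The method is described as "Using a one-sided Z test with pooled variance to test the difference between two independent proportions", and the conclusion is that "the study has over 80% power to detect a difference of 6.1% in STI incidence between the two conditions". The sample size comes from the H1a paragraph: "with 228 cases in each condition at baseline (or 185 at the final assessment timepoint in each condition".

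The measures listed in section 10(c) include no item on a chlamydia or gonorrhoea diagnosis made elsewhere, and no linkage to clinic or health-department records for outcomes. Section 4(b) reports that in the first efficacy trial "the incidence of (self-reported) STIs in Familias Unidas was significantly lower", a post hoc result.

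**The concern.** The power input and the endpoint are different quantities. Compounding an annual incidence gives the proportion infected at any time in three years. The endpoint gives the proportion with a detectable infection on at least one of four test days. The two agree only if every infection lasts until the next test, which may be 12 months away. Participants are recruited from paediatric clinics and both infections are treatable, so some will plausibly be diagnosed and treated, or will clear, between visits.

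Two things are at stake. The claim of over 80% power rests on a control rate that the endpoint may not be able to reach. And a result reported as incidence would be read as covering all infections, when it covers those found at scheduled visits.

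**Working it through.** **Inputs from section 12(a).** Annual rate 3.16%; control proportion 9.2%; difference 6.1 points, so the intervention arm is 9.2 − 6.1 = 3.1%; 228 per arm at baseline and 185 at month 36; one-sided pooled Z test. Alpha is not stated for this test; 0.05 is assumed.

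**Reproducing the plan.**
- 1 − (1 − 0.0316)³ = 0.0918, the plan's 9.2%. There is no term for detection.
- 228 × 0.95⁴ = 185.7, the plan's 185.
- Cohen's h = 2·asin√0.092 − 2·asin√0.031 = 0.262, the plan's 0.26.
- Power = Φ{[(p₁ − p₂) − 1.645·√(2p̄(1 − p̄)/n)] / √([p₁(1 − p₁) + p₂(1 − p₂)]/n)}. With p₁ = 0.092, p₂ = 0.031, p̄ = 0.0615 and n = 185: (0.061 − 1.645 × 0.02498)/0.02478 = 0.80, so power is 78.9%. The arcsine version gives 81.0%, and 228 per arm gives 85.9%. The plan's statement is reproduced to within about a point, with no slack: the pooled test needs 191 per arm for 80%.

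**What four visits can detect.** Duration of infection is not in the documents, so this step is an assumption range. Take a constant hazard and an exponential infected time with mean D years, ended by treatment or clearance. A gap of g years contributes D(1 − e^(−g/D)) years of detectable onset. Over gaps of 0.5, 0.5, 1 and 1 year:

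S = 2D(1 − e^(−0.5/D)) + 2D(1 − e^(−1/D)), and the detected fraction is S/3.

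For D = 0.25: S = 2(0.2162) + 2(0.2454) = 0.923, fraction 0.308.

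The control hazard is −ln(1 − 0.0316) = 0.0321 a year. The intervention hazard that gives 3.1% in three years is −ln(1 − 0.031)/3 = 0.0105 a year. Each arm's observable proportion is 1 − exp(−hazard × S). Both arms lose infections, and the planned relative effect (3.1/9.2 = 0.34) is nearly preserved.

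| Assumed mean duration | S (years) | Fraction | Control | Intervention | Power, 185 per arm |
|---|---|---|---|---|---|
| 3 months | 0.923 | 0.308 | 2.9% | 1.0% | 38.9% |
| 6 months | 1.497 | 0.499 | 4.7% | 1.6% | 53.5% |
| 12 months | 2.051 | 0.684 | 6.4% | 2.1% | 64.8% |
| 24 months | 2.459 | 0.820 | 7.6% | 2.5% | 71.6% |
| 36 months | 2.622 | 0.874 | 8.1% | 2.7% | 73.9% |
| No loss (plan) | 3 | 1 | 9.2% | 3.1% | 78.9% |

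**Check without a duration model.** Multiplying 9.2% and 3.1% by a detected fraction of 0.9, 0.7, 0.5 or 0.3 gives control rates of 8.3%, 6.4%, 4.6% and 2.8%, and power of 75%, 65%, 52% and 37%. The loss does not depend on the exponential form.

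**The case against.** The strongest reply is that the direction of the error is not known. The plan does not say whether 3.16% counts all infections or only diagnosed ones. If only diagnosed ones, testing every participant with an assay described as sensitive in asymptomatic patients could find infections that routine statistics miss, and the observed rate could be higher than the table shows. This stands, and it is why no single replacement for 9.2% is offered. It does not rescue 9.2%: a count of diagnosed cases includes those found in ordinary care, and the endpoint does not record these when they are diagnosed and treated between visits.

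It also stands that the durations are assumed and nothing in the documents favours 3 months over 24; that the rate is for ages 15 to 19 while enrolment is at 12 to 16; and that the definition in section 12(a) is open about counting positives at visits. Laboratory confirmation is a defensible choice over the self-report of the first trial. The full item text of the sexual-behaviour and community-services instruments is not given, so a relevant question may already exist; none is described and none enters the endpoint.

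Three stronger readings are tempting and are not supported. A reader might infer that a 6.1-point difference becomes impossible because it exceeds a control rate of 2.9% or 4.7%. That holds the absolute difference fixed while shrinking one arm; missed infections lower both arms, and the consequence is lost power. A reader might infer that H1c cannot be tested validly. The visit schedule is the same in both arms, so equal misses do not invalidate the randomised comparison. A reader might infer that the programme will bring earlier care and so produce a false benefit. That is possible, since only one arm has facilitator contact, but no document links the programme to earlier STI care or gives a size.

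**Conclusion.** The point holds as a mismatch between the power input and the endpoint, together with a label that promises more than is measured. Taking 3.16% at face value as the rate at which infections occur, any infection treated or cleared before the next test puts the observable control proportion below 9.2%. Over assumed mean durations of 3 to 36 months it lies between about 2.9% and 8.1%, with power between about 39% and 74%.

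These figures assume a constant 3.16% annual hazard, exponential duration, one-sided alpha 0.05, 185 participants per arm tested at all four visits, and the planned relative effect. Testing of everyone at every time point follows section 11; section 26 describes follow-up screening as indicated by reported risk behaviour, and section 10(c) counts five time points in the endpoint where section 12(a) counts four. These passages must be reconciled before any control rate is fixed. The net error against the true rate remains open, and differential care between the arms is a possible but unquantified source of bias.

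**What to change.** 1. Keep the laboratory result as the H1c endpoint and call it 'infection detected at scheduled visits', also where H2c uses it as an outcome.
2. State what the 3.16% counts: all infections or diagnosed cases.
3. Replace the single 9.2% and the claim of over 80% power with a range of control rates that the four visits could detect, the matching power, and the alpha used.
4. Unless an existing instrument already asks it, add one item to the follow-up youth survey: chlamydia or gonorrhoea diagnosed or treated elsewhere since the last assessment, with the date. Use it in a supporting analysis of laboratory-positive or diagnosed between visits.

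The cost is one survey item, one extra tabulation and, if 3.16% counts all infections, a lower stated power. The added item is self-report by participants who know their arm and could itself differ between arms, so that analysis is supportive only and the laboratory result stays primary.
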